7.3 TREATMENT COMPLIANCE

Treatment compliance will not be analysed as a specific endpoint. Any deviations from complete intake will be addressed in the RPM/DBLM (cf. [Section 6.2](#)) and described in the CTR.

7.4 PRIMARY ENDPOINT

The analysis of secondary endpoints will be based on the PKS.

Analysis of absolute oral bioavailability of dose normalised primary endpoints will be performed as defined in Section 7.1 and 7.3.1 of the CTP.

The statistical model for the primary analysis defined in the CTP is an analysis of variance (ANOVA) model on the logarithmic scale.

Primary PK endpoints will also be assessed descriptively. The analysis of standard PK parameters is performed according to BI standards ([4](#)) [001-MCS-36-472_RD-01].

Exclusion of PK parameters

The ADS ADPP contains column variables APEXC and APEXCO indicating inclusion/exclusion (APEXC) of a PK parameter and an analysis flag comment (APEXCO). All analyses based on the PKS are based on PK parameter values which are not flagged for exclusion, i.e. with APEXC equal to "Included".

Exclusion of plasma concentrations

The ADS ADPC (PK concentrations per time-point or per time-interval) contains column variables ACEXC or ACEXCO indicating inclusion/exclusion (ACEXC) of a concentration

and an analysis flag comment (ACEXCO). Exclusion of a concentration depends on the analysis flag comment ACEXCO. For example, if ACEXCO is set to "ALL CALC", the value will be excluded for all types of analyses based on concentrations. If ACEXCO is set to "DESC STATS" the value will be excluded from descriptive evaluations per planned time point/time interval. If ACEXCO contains the addition "TIME VIOLATION" or "TIME DEVIATION", the value can be used for further analyses based on actual times. If ACEXCO is set to "HALF LIFE", the value will be excluded from half-life calculation only; the value is included for all other analyses. Excluded concentration itself will be listed in the CTR associated with an appropriate flag.

Further details are given in "Noncompartmental Pharmacokinetic / Pharmacodynamic Analyses of Clinical Studies" (4) and "Description of Analytical Transfer Files and PK/PD Data Files" (6).

7.5 SECONDARY ENDPOINT

Not applicable

7.6 FURTHER ENDPOINTS

7.6.1 Safety parameters

Safety and tolerability will be analysed as described in Section 7.8 of this TSAP.

7.7 EXTENT OF EXPOSURE

Only descriptive statistics are planned for this section of the CTR.

7.8 SAFETY ANALYSIS

All safety analyses will be performed on the TS.

7.8.1 Adverse events

The analyses of AEs will be descriptive in nature. All analyses of AEs will be based on the number of subjects with AEs and not on the number of AEs.

For analysis, multiple AE occurrence data on the eCRF will be collapsed into one event provided that all of the following applies:

- All AE attributes are identical (lower level term, intensity, action taken, therapy required, seriousness, reason for seriousness, relationship, outcome, AESI)
- The occurrences were time-overlapping or time-adjacent (time-adjacency of two occurrences is given if the second occurrence started at most 1 hour after the first occurrence ended)

For further details on summarization of AE data, please refer to "Analysis and Presentation of Adverse Event Data from Clinical Trials" (7) and "Handling of missing and incomplete AE dates" (3).

The analysis of AEs will be based on the concept of treatment emergent AEs. That means that all AEs will be assigned to the screening or on-treatment phase as defined in [Section 6.1](#). AEs will be analysed based on actual treatments, as defined in [Table 6.1: 1](#).

An overall summary of AEs will be presented. This overall summary will comprise summary statistics for the class of other significant AEs according to ICH E3 (8) and for the class of AESIs.

CTP: *The following are considered as AESIs:*

Hepatic injury

A hepatic injury is defined by the following alterations of hepatic laboratory parameters:

- *An elevation of AST (aspartate transaminase) and/or ALT (alanine transaminase) ≥ 3 -fold ULN combined with an elevation of total bilirubin ≥ 2 -fold ULN measured in the same blood sample, or*
- *Aminotransferase (ALT, and/or AST) elevations ≥ 10 -fold ULN.*

The investigator had to classify on the eCRF whether an observed AE was an AESI or not.

According to ICH E3 (8), AEs classified as "other significant" need to be reported and will include those non-serious and non-significant AEs

- (i) which are marked haematological or other lab abnormalities, or
- (ii) which were reported with "action taken = discontinuation" or "action taken = reduced", or
- (iii) which lead to significant concomitant therapy as identified by the Clinical Monitor/Investigator at a Medical Quality Review Meeting.

The frequency of subjects with AEs will be summarised by treatment, primary SOC and preferred term. AEs which were considered by the investigator to be drug related will be summarised separately. Separate tables will also be provided for subjects with SAEs, subjects with AESIs and subjects with other significant AEs (according to ICH E3 (8)). The frequency of subjects with AEs and the frequency of subjects with AEs considered by the investigator to be drug related will also be summarised by maximum intensity, primary SOC and preferred term.

The system organ classes and preferred terms within system organ classes will be sorted by descending frequency overall treatment groups.

For disclosure of AE data on ClinicalTrials.gov, the frequency of subjects with non-serious AEs occurring with an incidence of greater than 5 % (in preferred terms) will be summarised by treatment, primary SOC and preferred term. The frequency of subjects with SAEs will also be summarised.

For disclosure of AE data in the EudraCT register, the frequency of AEs, the frequency of non-serious AEs with an incidence of greater than 5 % (in preferred terms) and the frequency of SAEs will be summarised.

For support of lay summaries, the frequency of subjects with drug-related SAEs will be summarised by treatment, primary system organ class and preferred term.

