Since preclinical data indicate that BI 730357 has phototoxicity potential, direct exposure to the sun or exposure to solarium radiation is not allowed during the entire study, and use of sunscreens is mandatory in that time (see [Section 4.2.2.2](#)).

As with other immune-targeted therapies, impaired host defense is a theoretical target-related toxicity, potentially resulting in increased risk of infection and/or malignancy. Th17 cells play an important role in defense against extracellular bacteria and fungi at mucosal surfaces [[R16-3166](#), [R16-3149](#)]. IL-17 antagonists are associated with increased infections [[R13-2643](#)]. Homozygous, but not heterozygous ROR γ knockout mice have a high incidence of T-cell lymphoma, thought to originate in the thymus [[R16-2630](#)]. While the translatability of the knockout phenotype to pharmacological ROR γ antagonism and to humans is unknown, this raises the hypothetical concern for clinical T-cell lymphoma risk. The exact cause of T-cell lymphomas in ROR γ knockout mice is not fully understood, but changes in homeostasis in the thymus, such as thymocyte apoptosis and proliferation, are thought to play a role. AEs and SAEs consistent with malignancy, and specifically those representing lymphoma, are to be carefully monitored and evaluated throughout the BI 730357 clinical development program, and monitoring of peripheral blood lymphocyte subsets integrated into clinical trials.

As with all drugs, the potential for hypersensitivity and allergic reactions has to be taken into consideration when BI 730357 is administered.

Risks related to intravenous administration of BI 730357 BS (C-14) solution

No intravenous route is planned for therapeutic use of BI 730357. Therefore, in accordance with the guideline on non-clinical safety studies on microdose trials (ICH-M3(R2), [[R15-0594](#)]), the intravenous microtracer dose of 100 µg BI 730357 BS (C-14) is considered

Proprietary confidential information © 2018 Boehringer Ingelheim International GmbH or one or more of its affiliated companies

to be adequately qualified by the existing oral toxicity studies where adequate exposure margins have been reached. An investigation of intravenous local tolerance of the drug substance is not recommended in this situation because the administered dose is very low (100 µg maximum) and no novel i.v. vehicle is used.

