5.2.6.1.4 Adverse events of special interest

The term adverse events of special interest (AESI) relates to any specific AE that has been identified at the project level as being of particular concern for prospective safety monitoring and safety assessment within this trial, e.g. the potential for AEs based on knowledge from other compounds in the same class. AESIs need to be reported to the sponsor’s Pharmacovigilance Department within the same timeframe that applies to SAEs, please see Section [5.2.6.2.2](#).

The following are considered as AESIs:

- Hepatic injury
A hepatic injury is defined by the following alterations of hepatic laboratory parameters:
 - An elevation of AST (aspartate transaminase) and/or ALT (alanine transaminase) ≥ 3 -fold ULN combined with an elevation of total bilirubin ≥ 2 -fold ULN measured in the same blood sample, or
 - Aminotransferase (ALT, and/or AST) elevations ≥ 10 -fold ULN

These lab findings constitute a hepatic injury alert and the subjects showing these lab abnormalities need to be followed up according to the ‘DILI checklist’ provided in the

ISF. In case of clinical symptoms of hepatic injury (icterus, unexplained encephalopathy, unexplained coagulopathy, right upper quadrant abdominal pain, etc.) without lab results (ALT, AST, total bilirubin) available, the Investigator should make sure that these parameters are analysed, if necessary in an unscheduled blood test. Should the results meet the criteria of hepatic injury alert, the procedures described in the DILI checklist should be followed.

- Severe infections (grading according to Rheumatology Common Toxicity Criteria (RCTC) developed by OMERACT [[R13-3515](#)])
- Opportunistic and mycobacterium tuberculosis infections

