4. CHANGES IN THE PLANNED ANALYSIS OF THE STUDY

All analyses described in this TSAP are in accordance with the statistical methods described in the CTP.

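### Does the hepatic-only AESI list in SAP 7.8.1 keep infection events out of the safety tables?

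*SAP*

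**What the plan says.** Protocol 5.2.6.1.4 names three kinds of AESI. The first is hepatic injury, set out by laboratory criteria ("A hepatic injury is defined by the following alterations of hepatic laboratory parameters"). The second is "Severe infections (grading according to Rheumatology Common Toxicity Criteria (RCTC) developed by OMERACT"). The third is "Opportunistic and mycobacterium tuberculosis infections", followed by a long list of organisms and conditions.

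SAP 7.8.1 marks its text as taken from the protocol, begins with "The following are considered as AESIs", and reproduces the hepatic category with its two laboratory criteria. Neither infection category appears. The next sentence reads "The investigator had to classify on the eCRF whether an observed AE was an AESI or not".

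The same SAP section plans two AESI outputs: an AESI class within the overall adverse event summary, and a separate table, named alongside others as "subjects with AESIs and subjects with other significant AEs". SAP Section 4 declares no departure from the protocol: "All analyses described in this TSAP are in accordance with the statistical methods described in the CTP".

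**The concern.** A SAP is meant to tell the programmer what goes into each table. Here its only description of the AESI class covers one of the protocol's three categories. Read as an operational definition, it would confine the AESI outputs to liver events.

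The missing categories are not peripheral. Protocol 1.4 says of this drug class that "impaired host defense is a theoretical target-related toxicity, potentially resulting in increased risk of infection and/or malignancy", and a positive tuberculosis test is a trial-specific exclusion criterion in Protocol 3.3.3. The liver category that survives is the more general one.

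With 6 to 8 subjects, a single event is a large percentage. If an infection AESI were reported under the protocol and left out of the table, the report would show none where there was one. SAP Section 4 gives no sign that a narrower definition was intended.

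**Working it through.** No sample size, power or error rate is involved, so the check is a comparison of texts and then a look at which variable drives the tables.

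**Step 1: compare the definitions.**

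| Category | Protocol 5.2.6.1.4 | SAP 7.8.1 |
|---|---|---|
| Hepatic injury | yes | yes |
| Severe infections (RCTC grading) | yes | no |
| Opportunistic and tuberculosis infections | yes | no |

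The protocol has 3 categories and the SAP 1, so 2 of 3 (67%) are missing. The discrepancy is real. This is a count of headings, however, and does not measure any effect on results.

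**Step 2: find what makes an event an AESI in the data.** Under SAP 7.8.1, status is the investigator's classification on the eCRF. The rule in that section for collapsing repeated occurrences also treats AESI as a recorded attribute of the event, beside intensity and seriousness. It is a data field and is not derived from the list in the SAP.

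**Step 3: find which definition the investigator applies.** The investigator works under the protocol. Protocol 5.2.6.2.1 requires all AESIs to be documented on the CRF, and Protocol 5.2.6.2.2 requires them to reach the sponsor within 24 hours. Both rest on the three-category definition.

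**Step 4: look for a filter between the flag and the table.** The overall summary refers to AESIs as a class, and the separate table counts subjects with AESIs. Neither is restricted by category, and nothing in the SAP tells the programmer to drop flagged events that are not hepatic. Protocol 7.3.4, on which the SAP says it is based, asks for AESIs to be listed separately and refers to Protocol 5.2.6.1, where the full definition stands.

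**Step 5: put one event through.** Take one treated subject with an infection flagged as an AESI, with onset in the on-treatment phase.

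- With 6 treated: 1/6 = 16.7%.
- With 8 treated: 1/8 = 12.5%.
- With a hepatic-only filter: 0/6 or 0/8 = 0%.

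The third line needs a step that the SAP does not contain. Followed as written, the SAP gives the first or second line.

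**Step 6: check the other displays.** SAP 7.8.1 tabulates all adverse events by system organ class and preferred term, and again by maximum intensity. Drug-related events and serious events have their own tables. SAP Section 7 has individual values listed for all subjects. An infection would be visible in these whether or not it was flagged.

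**The case for a change.** The best case for acting is that the SAP never says whether the eCRF flag or its own list governs if the two disagree. A validator could query a flagged infection as outside the stated definition, a programmer could footnote the table as hepatic only, and a reader could take an empty AESI table as reassurance about the liver alone. The general tables are also an imperfect substitute: they use the protocol's ordinary mild, moderate and severe scale rather than RCTC grading, and they do not mark which infections are AESIs.

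Some of this stands. The quotation is incomplete, and a hepatic-only footnote is possible. Nothing in the extracted text suggests a redaction at that point, though a loss in reading the PDF cannot be wholly excluded.

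The rest does not carry through to a result. The hepatic text is labelled as a protocol citation, so anyone who meets a conflict knows which source to open. SAP Section 3 assumes the reader knows the protocol. The sentence straight after the list names the eCRF classification as the basis. SAP Section 4 speaks of statistical methods, and a shortened quotation of a clinical definition alters none while events are counted from the flag. Showing AESIs by category would be a matter of preference: neither document asks for it, and preferred terms already tell an infection from a liver event in a trial this small.

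**Conclusion.** The mismatch is genuine but clerical: two of the protocol's three AESI categories are missing from a quotation in SAP 7.8.1. The inference that infection AESIs would be left out of the tables does not follow, because those tables rest on the investigator's flag, the flag rests on the protocol's definition, and the SAP sets no category filter.

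The effect on planned results is nil. Safety analysis is descriptive with no testing (Protocol 7.3.4), and the primary endpoint, AUC from zero to infinity, is untouched. Data collection and expedited reporting follow the protocol whatever the SAP quotes.

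This rests on two assumptions: that investigators flag AESIs by the protocol's three categories, and that programmers count from the flag as SAP 7.8.1 describes. Both are what the documents say. Completing the citation would be tidy, but it would change no table and no conclusion, so the point does not call for a change to the plan.

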7.8.2 Laboratory data

The analyses of laboratory data will be descriptive in nature and will be based on BI standards "Display and Analysis of Laboratory Data" ([9](#)).

Analyses will be based on normalised values, which means transforming to a standard unit and a standard reference range. The original values will be analysed if the transformation into standard unit is not possible for a parameter.

Descriptive statistics of laboratory values over time and for the difference from baseline (see [Section 6.7](#)) will be provided.

Possibly clinically significant abnormal laboratory values are only those identified either in the Investigator's comments or at the RPM/DBLM at the latest. It is the Investigator's responsibility to decide whether a lab value is clinically significant abnormal or not. Standard or project-specific rules for flagging clinically significant values in an automated manner will not be applied in this study.

Clinically relevant findings in laboratory data will be reported as baseline conditions (at screening) or as AEs (during the trial) if judged clinically relevant by the investigator, and will be analysed as such.

7.8.3 Vital signs

The analyses of vital signs (blood pressure and pulse rate) will be descriptive in nature. Descriptive statistics of vital signs over time and for the difference from baseline (see [Section 6.7](#)) will be provided.

Clinically relevant findings in vital signs data will be reported as baseline conditions (at screening) or as AEs (during the trial) if judged clinically relevant by the investigator, and will be analysed as such.

7.8.4 ECG

Abnormal findings in 12-lead ECG will be reported as baseline conditions (at screening) or as AEs (during the trial) if judged clinically relevant by the investigator, and will be analysed as such. No separate listing or analysis of ECG data will be prepared.

7.8.5 Others

Local tolerability

Clinically relevant findings from the local tolerability assessment will be reported as AEs.

Physical examinations

Physical examination findings will be reported as relevant medical history/baseline condition (i.e., a condition already existent before intake of first study drug) or as AE and will be summarised as such. No separate listing or analysis of physical examination findings will be prepared.

10. HISTORY TABLE

Table 10: 1 History table

Version	Date (DD-MMM-YY)	Author	Sections changed	Brief description of change
Final	17-APR-19		None	This is the final TSAP without any modification
